3.3.2 Total Number of Study Sites/Total Number of Subjects Projected

The study will be conducted at The Children's Hospital of Philadelphia.

This study is a clinical investigation of the anterior vertebral tethering procedure in up to 40 subjects using the investigational device elements as described within this protocol. Based on a broad review of patient visits over the past year, we may expect to enroll about 5-10 patients per year.

3.4 Study Population

3.4.1 Inclusion Criteria

- 1) Males or females age 8 to 16 years old at time of enrollment (inclusive)
- 2) Diagnosis of idiopathic scoliosis
- 3) Sanders bone age of less than or equal to 4
- 4) Thoracic curve of greater than or equal to 35 degrees and less than or equal to 60 degrees
- 5) Lumbar curve less than 35 degrees
- 6) Patient has already been identified for and recommended to have surgical intervention
- 7) Spina bifida occulta is permitted
- 8) Spondylolysis or Spondylolisthesis is permitted, as long as it is non-operative, the patient has not had any previous surgery for this, and no surgery is planned in the future
- 9) Completed standard-of-care procedures, as outlined in the Table of Study Procedures
- 10) Subject consent and (if applicable) assent

3.4.2 Exclusion Criteria

- 1) Pregnancy (current)
- 2) Prior spinal or chest surgery
- 3) MRI abnormalities (could include syrinx greater than 4mm, Chiari malformation, or tethered cord)
- 4) Neuromuscular, thoracogenic, cardiogenic scoliosis, or any other non-idiopathic scoliosis
- 5) Associated syndrome, including Marfan syndrome or neurofibromatosis
- 6) Sanders bone age greater than 4
- 7) Thoracic curve less than 35 degrees or greater than 60 degrees
- 8) Lumbar curve greater than or equal to 35 degrees
- 9) Unable or unwilling to firmly commit to returning for required follow-up visits

10) Investigator judgement that the subject/family may not be a candidate for the intervention

Subjects that do not meet all of the enrollment criteria may not be enrolled. Any violations of these criteria must be reported in accordance with IRB Policies and Procedures.

4 STUDY PROCEDURES

4.1 Screening Phase

4.1.1 Visit 1 (Screening & Pre-operative Visit)

- Informed consent/assent
- Medical record and x-ray review for eligibility screening (research)
- History and physical exam with height and weight
- Research specific physical exam (research)
- Anesthesia evaluation
- Pulmonary function test (completed at treating physician's discretion)
- Bloodwork (outlined in Section 5.1.6)
- Pregnancy test, as applicable
- X-ray: bending bolster, AP/PA, lateral spine, and hand bone age
- SRS 30 Questionnaire (research)
- Clinical photographs (research)
- Medical record and x-ray information abstraction (research)

4.2 Study Treatment Phase (Surgery)

4.2.1 Visit 2 (Surgical Intervention)

This phase includes the surgical intervention - vertebral body tethering through anterior thoracoscopic approach under general anesthesia and fluoroscopic guidance. This process is described in Section 2.

Data from the surgery will be abstracted by medical record review for adverse events or complications. Intra-operative data (including radiographs) will also be abstracted from the medical record/surgical logs. Results from the surgery and inpatient stay will be abstracted at the time of discharge, except for those events which fall under the reporting guidelines of AE/SAEs. All AE/SAEs will be reported according to reporting guidelines listed in Section 8.

4.3 Post-surgical Follow-up Phase

This phase will include monitoring for post-operative complications/SAE, as well as three SOC clinical visits in this phase, where the subject will also undergo a research visit. This phase also includes all inpatient recovery in the post-operative period, which includes post-operative bloodwork and radiographs. Information from SOC procedures will also be abstracted from the medical records and radiology databases.

4.3.1 Visit 3 (POD 21)

- X-ray: AP/PA and lateral spine (completed at treating physician's discretion)
- History and physical exam with height and weight
- Medical record review and abstraction (research)
- Complications review (research)

4.3.2 Visit 4 (POD 45)

- X-ray: AP/PA and lateral spine
- X-ray: Bending bolster films (completed at treating physician's discretion)
- History and physical exam with height and weight
- Research specific physical exam (research)
- Medical record review and abstraction (research)
- X-ray review and abstraction (research)
- Complications review (research)

4.3.3 Visit 5 (POD 90)

- X-ray: AP/PA and lateral spine
- X-ray: Bending bolster films (completed at treating physician's discretion)
- History and physical exam with height and weight
- Research specific physical exam (research)
- Medical record review and abstraction (research)
- X-ray review and abstraction (research)
- Complications review (research)

4.4 Extended Follow-up Phase

This phase will include monitoring for post-operative complications/SAEs, as well as three SOC clinical visits in this two year phase, where the subject will also undergo a research visit. Information from SOC procedures will also be abstracted from the medical records and radiology databases.

4.4.1 Visit 6 (POD 180)

- X-ray: AP/PA and lateral spine
- X-ray: Bending bolster films (completed at treating physician's discretion)
- History and physical exam with height and weight
- Research specific physical exam (research)
- Medical record review and abstraction (research)
- X-ray review and abstraction (research)
- Complications review (research)
- Clinical photographs (research)
- SRS 30 Questionnaire (research)

4.4.2 Visit 7 (POD 365)

- X-ray: AP/PA and lateral spine
- X-ray: Bending bolster films (completed at treating physician's discretion)
- Pulmonary function test (completed at treating physician's discretion)
- History and physical exam with height and weight
- Research specific physical exam (research)
- Medical record review and abstraction (research)
- X-ray review and abstraction (research)
- Complications review (research)
- Clinical photographs (research)
- SRS 30 Questionnaire (research)

4.4.3 Visit 8 (POD 730)

- X-ray: AP/PA and lateral spine
- X-ray: Bending bolster films (completed at treating physician's discretion)
- Pulmonary function test (completed at treating physician's discretion)
- History and physical exam with height and weight
- Research specific physical exam (research)
- Medical record review and abstraction (research)
- X-ray review and abstraction (research)
- Complications review (research)
- Clinical photographs (research)
- SRS 30 Questionnaire (research)
- Study completion CRF (research)

4.5 Long-Term Follow-up Phase

We are planning a long-term follow-up phase (LTFU) through approximately two years after each subject reaches skeletal maturity. Following the extended follow-up phase (approximately two years post-operative), the LTFU will be an observational study involving chart review. This will be performed under a separate research study. Device-related SAEs and relevant data to assess safety and feasibility endpoints up to two years after skeletal maturity will be reported in accordance with FDA requirements.

4.6 Unscheduled Visits

Unscheduled clinic visits will be made through the department's/hospital's clinical schedulers. As part of clinical care, physical evaluations and tests may be conducted. At these visits, the only research procedures performed will be medical record/radiographic record abstraction and complications review.

4.7 Subject Completion/Withdrawal

Subjects may withdraw from the study at any time without prejudice to their care. They may also be discontinued from the study at the discretion of the Investigator for lack of adherence to study treatment or visit schedules, AEs, or due to non-compliance. However, in order to collect important study-related data for this investigational device, as much as is feasible, the Investigator and study team will make efforts to follow-up subjects who do not strictly adhere to timely visit schedules. The Investigator and study team may do this via emails, phone calls, or letters. The Investigator may also withdraw subjects who violate the study

plan, or to protect the subject for reasons of safety or for administrative reasons. It will be documented whether or not each subject completes the clinical study. If the Investigator becomes aware of any serious, related adverse events after the subject completes or withdraws from the study, they will be recorded in the source documents and on the CRF.

Subjects who are withdrawn from the study during the post-operative follow-up phases due to AEs/SAEs, such as tether failure or implant re-operation, will no longer be followed at study-specific visits. These subjects have the option to consent and allow for continued monitoring by medical and radiographic record review through the end of the two-year Extended Follow-up Phase. Subjects who are withdrawn from the study also have the option to enroll in a separate LTFU observational study.

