4.7.1 Early Termination Study Visit

Subjects that withdraw from the study prior to study completion will have all data collected to date kept on file. Subjects who wish to be withdrawn from the study may do so, preferably by submitting a written request addressed to the site's PI. A 'Study Completion CRF' will be filed for each subject.

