5.3 Efficacy Evaluation

This is a safety and feasibility clinical trial. A therapeutic exploratory endpoint for this VBT procedure will be measurement of the Cobb angle. The Cobb angle is a coronal plane radiographic measurement of curvature of the spine. This angle will be recorded for the pre-operative coronal spine radiograph, as well as all subsequent serial radiographs. The change

in Cobb angle (reduction) will be the primary exploratory therapeutic evaluator of efficacy. ‘Success’ of the intervention will be defined by a final Cobb angle of less than or maintained at less than 50 degrees, for curves which were less than 50 degrees pre-operatively. For curves which were greater than 50 degrees pre-operatively, a Cobb angle which is less than or maintained at less than 50 degrees is considered a ‘success’.

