5.4 Chart Review for Withdrawn Subjects

Subjects who are withdrawn from the study during the follow-up phase due to AEs/SAEs will no longer follow the study visit schedule nor participate in study-specific procedures. These subjects have the option to consent and allow for continued monitoring by medical and radiographic record review through the end of the two-year Extended Follow-up Phase. Subjects who are withdrawn from the study also have the option to enroll in a separate LTFU observational study.

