6.3.3 Efficacy Analysis

This initial clinical study using the Anterior Vertebral Tether Device for pediatric idiopathic scoliosis is focused on safety and feasibility, not efficacy, as primary endpoints. There will be an exploratory therapeutic endpoint, Cobb angle change, based on an intention to treat approach and will include all subjects who have undergone the intervention.

The exploratory therapeutic endpoint used for efficacy will be change in post-operative Cobb angle compared to pre-operative Cobb angle, measured on coronal radiograph of the spine. Considering change in Cobb angle is a continuous variable, a t-test will be used to detect any change in Cobb angle post-operatively. Linear regression will be utilized to assess which variables are associated with change in post-operative Cobb angle.

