6.6.2 Stopping rules for SAEs that are device-related

Definition of Terms:

- Screw failure – screw, locking caps, and/or centering staple have loosened from the vertebra AND require re-operation.
- Tether failure – the tether has broken or lost tension. Diagnosed at any time point after 3 months by increased angulation at a disc space on standing PA radiograph or increase in disc wedging on side bending x-ray to the side away from the implant. Also, it is only an SAE if noted before maturity, overall Cobb angle worsens compared to the first erect measurement, AND requires re-operation.
- Implant re-operation - any problem with the implant that requires re-operation including re-operation for overcorrection with any of the following: a removal of all or part of the implant, loosening of the tension on the implant, or spinal fusion.

Stopping Rules

- Screw/locking cap/staple failure stopping point: 3 of first 5 cases, 5 of first 10, or in greater than 50% of cases 15 and beyond.
- Tether failure stopping point: 3 of first 5 cases, 5 of first 10, or greater than 50% of cases 15 and beyond.
- Implant failure re-operation stopping point: occurs in 3 of first 5, 5 of first 10, or greater than 50% of cases 15 and beyond.

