9.5 Informed Consent/Assent and HIPAA Authorization

After the subject has made the decision to have surgery and discussed this decision with their doctor, potential subjects who may satisfy the inclusion/exclusion criteria will be identified by the clinical staff, who will contact a study team member. Eligible patients will then undergo consent/assent during their orthopedic visit. This will take place in a private exam room in the clinic. The study will be explained to the patients/families and they can decide whether to participate in the study. Subjects and their families will be given the opportunity to ask questions and may take as long as they need to make a decision.

For subjects that are withdrawn from the study due to AEs/SAEs, as determined by the investigator, they will undergo consent/assent during their orthopedic visit to decide whether they agree to review of medical and radiographic records following the occurrence of the AE/SAE up to two years post-operatively.

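### Two-year films after withdrawal for tether failure or re-operation depend on a new optional consent; separately, the success definition in 5.3 can credit a later fusion to the tether

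*Combined protocol and SAP*

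**What the plan says.** **Follow-up after withdrawal.** Section 4.7 provides that subjects withdrawn in the post-operative follow-up phases because of AEs/SAEs, "such as tether failure or implant re-operation, will no longer be followed at study-specific visits". Section 5.4 repeats the rule and adds: "These subjects have the option to consent and allow for continued monitoring by medical and radiographic record review", up to the end of the two-year phase. Section 9.5 shows that this is a fresh decision taken after the event: "they will undergo consent/assent during their orthopedic visit to decide whether they agree to review of medical and radiographic records". The separate long-term study is also offered, again as an option (4.7, 5.4).

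**What is kept regardless.** Subjects who withdraw "will have all data collected to date kept on file" (4.7.1). Section 4.7 also has a fallback: "If the Investigator becomes aware of any serious, related adverse events after the subject completes or withdraws from the study", these are entered in the source documents and on the CRF.

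**What the results need.** The Cobb analysis in 6.3.3 is "based on an intention to treat approach and will include all subjects who have undergone the intervention". The synopsis stresses the Cobb angle at POD 730 and lists progression beyond 50 degrees at two years among the extended-phase evaluations. In the same item it lists over-correction, implant failure and re-operation.

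**Success.** For curves below 50 degrees before surgery, success "will be defined by a final Cobb angle of less than or maintained at less than 50 degrees" (5.3). The same threshold applies to curves that started above 50. Section 6.6.2 foresees that implant re-operation may consist of "a removal of all or part of the implant, loosening of the tension on the implant, or spinal fusion".

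**The concern.** These are two independent gaps. The first makes data missing. The second concerns how data that are present are classified.

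1. The examples that 4.7 gives for withdrawal are device failures. The subjects most likely to lose their two-year film are therefore selected by how the device performed, and neither 6.3.3 nor any other section says how a missing film is handled. The commitment to analyse all operated subjects cannot be met for anyone who is withdrawn and does not give the new consent.

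2. Section 5.3 looks only at the last angle. It does not ask whether the tether or a later operation produced it.

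The results at stake are exploratory and extended-phase: success, progression beyond 50 degrees, and Cobb change at two years. These data have planned uses. Section 6.4 plans a comparison of clinical outcomes by intervention with the Harms Study Group data, which 1.1.2.1 describes as a registry of fusions. Section 9.1 sends a data set to the manufacturer for its HDE submission. Neither section says that the success label will be used, but a fused subject credited to the tether would blur a tether-versus-fusion contrast.

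**Working it through.** **Inputs.** N = 40 is the maximum in 6.4. The documents give no rate of tether failure, re-operation, withdrawal or refused consent, so every count below is an assumption.

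**The plan's own figure.** Section 6.4 states more than 80% power at n = 40 (paired t-test, two-sided 5%). The noncentrality is difference/SD × √n.
- Thoracic: 17.9/6.6 × √40 = 17.15, power about 100%.
- Lumbar: 6.5/5.38 × √40 = 7.64, power above 99.99%.
- With only 20 subjects, noncentrality is 12.13 and 5.40, and power is about 100% and 99.9%.

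The stated figure is true, and losing subjects does not threaten power. The issue is bias and classification.

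**Gap 1: m missing POD 730 films.** Each missing subject leaves 1/40 = 2.5 percentage points of the all-treated rate undetermined. Assume 2 of the subjects with films are at 50 degrees or more. Among subjects with films, success is (38 − m)/(40 − m). The all-treated rate lies between (38 − m)/40 and 38/40.

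| m | Subjects with films | All-treated range | Width |
|---|---|---|---|
| 4 | 34/36 = 94.4% | 85–95% | 10 points |
| 8 | 30/32 = 93.8% | 75–95% | 20 points |
| 12 | 26/28 = 92.9% | 65–95% | 30 points |

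The low ends require every missing subject to be a failure. At the high ends every missing subject is below 50 degrees, and the observed rate then understates the all-treated rate. The observed figure can err either way. The width for progression is also m/40.

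**Gap 2: f failed tethers fused to below 50 degrees, no films missing.** Suppose 5.3, read with post-re-operation films, gives 38/40 = 95.0% (exact 95% CI 83.1–99.4). Recounting the f subjects as non-successes gives (38 − f)/40.

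| f | Success | Exact 95% CI |
|---|---|---|
| 1 | 37/40 = 92.5% | 79.6–98.4 |
| 2 | 36/40 = 90.0% | 76.3–97.2 |
| 4 | 34/40 = 85.0% | 70.2–94.3 |

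**Cobb change.** No size is computed. Post-re-operation films could move the mean either way, because 6.6.2 includes re-operation for overcorrection.

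**Event capture.** Section 8.5 requires all SAEs of any cause and all device-related AEs to POD 730. The 4.7 fallback is narrower: serious, related events that the investigator learns of. The failure that led to withdrawal is already recorded, so only later events could be missed.

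**The case against.** **The success proportion has no planned analysis.** This stands. The synopsis treats the Cobb angle as continuous, 6.3.3 plans a t-test and linear regression on Cobb change, and section 6 never tests success. But 5.3 defines the measure, and a defined measure is likely to be reported.

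**Re-operation is already counted.** This also stands: it sits in the same synopsis item as progression, and a fusion for deformity would be captured there. It is not linked to the success definition, so a success figure quoted alone could still include fused subjects.

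**The gap is narrower than it looks.** Withdrawal after tether failure or re-operation is not automatic. The triggering event stays counted, data to date are kept, and the visits follow routine care (3.3.1), so films may exist. The long-term study may recover some information, but it is optional and is placed after the two-year phase (4.5), so the two-year film is not assured.

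**Stronger readings the documents do not support.**
- A reader might infer that a fused subject will necessarily be a success. Because final is undefined, a film from before re-operation could equally serve, and 8.4.1 defines the study intervention as the tethering surgery and implantation. The wording permits the misclassification; it does not require it.
- A reader might infer that missing films flatter the device. That holds only if the missing subjects do worse than those observed. If they have been fused to below 50 degrees, 5.3 read literally would count them as successes, and their absence lowers the observed rate.

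**Conclusion.** Both gaps are real and should be fixed. They affect exploratory and extended-phase results. They do not touch the primary objective, which 2.1 limits to safety in the immediate post-operative period, or implantation feasibility.

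Gap 1 follows directly from 4.7, 5.4 and 9.5 set against 6.3.3: two-year Cobb and progression data can be missing in relation to outcome, with unknown direction of bias. Gap 2 follows from silence in 5.3 combined with 6.6.2: a failed tether converted to fusion can count as a success.

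At N = 40 each gap is worth 2.5 points of the success rate per affected subject. The number of affected subjects is unknown, so the tables show sensitivity and do not predict an effect. The gap 2 table also assumes that the fused subjects are filmed and measure below 50 degrees.

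**What to change.** (a) Have the original consent cover medical and radiographic record review to POD 730 for all implanted subjects, including those withdrawn for AEs/SAEs, with the right to decline. Update consent for those already enrolled.

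(b) In 5.3, define final as the POD 730 film. Count conversion to fusion, or re-operation for tether or implant failure, before POD 730 as non-success, with all implanted subjects in the denominator. Show other re-operations, such as those for overcorrection, separately.

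(c) Report Cobb change for all treated subjects using available POD 730 films. Beside it, give a result in which re-operated subjects enter with the latest available film of any kind before re-operation, unscheduled films included. State that the two answer different questions.

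(d) Give the number of missing POD 730 films by reason, and show success and progression with the missing counted both ways.

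The cost is consent and protocol wording, updated consents and a little more analysis. No study visits are added. Some films will still be missing, because families may decline and routine films may fall outside the ±90-day window. The success figure may become less favourable.

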4.7.1 Early Termination Study Visit

Subjects that withdraw from the study prior to study completion will have all data collected to date kept on file. Subjects who wish to be withdrawn from the study may do so, preferably by submitting a written request addressed to the site's PI. A 'Study Completion CRF' will be filed for each subject.

4.8 Live Case Presentation

A live case demonstration may be performed for one subject's surgery. Selection of an eligible subject, consent process, conduct of the surgical procedure, and subsequent follow-up visits and monitoring will be performed as defined in the protocol and similarly to subjects who are not participating in the live case demonstration.

